## 7.4 CONCOMITANT MEDICATIONS, TREATMENTS AND PROCEDURES

All concomitant prescription medications including non-opiate medications taken at least 90 days before study enrollment and during study participation will be recorded on the case report forms (CRFs). For this protocol, a prescription medication is defined as a medication that can be prescribed only by a properly authorized/licensed clinician. Medications to be reported in the CRF are concomitant prescription medications, over-the-counter medications and non-prescription medications.

## 7.5 PROHIBITED MEDICATIONS, TREATMENTS AND PROCEDURES

The medications and substances listed below are prohibited for the specified time periods:

- **Buprenorphine**, either as part of a maintenance program or any illicit/non prescribed is prohibited for the duration of the study.
- **Methadone** is prohibited at least 14 days prior to Day 0 and for the duration of the Study.
- All other **opioids** are prohibited for the duration of the study unless approved by the PI or study clinician (see section 7.7)
- **Oral naltrexone** is prohibited for at least 30 days prior to Day 0 and for the duration of the study
- **Extended release naltrexone (e.g., Vivitrol)** is prohibited for at least 60 days prior to Day 0 and for the duration of the study unless administered under this trial protocol.

## 7.6 PROPHYLACTIC MEDICATIONS, TREATMENTS AND PROCEDURES

### 7.6.1 *Prophylactic Medications*

N/A

## 7.7 RESCUE MEDICATIONS, TREATMENTS AND PROCEDURES

Since NTX acts as an opioid blocker, participants requiring pain relief during the study period will be offered appropriate pain medications e.g., tramadol, regional blocks or partial opioid agonist such as buprenorphine.

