### 3. Precipitation of Opioid Withdrawal

The symptoms of spontaneous opioid withdrawal (which are associated with the discontinuation of opioid in a dependent individual) are uncomfortable, but they are not generally believed to be severe or necessitate hospitalization. However, when withdrawal is precipitated abruptly by the administration of an opioid antagonist to an opioid-dependent patient, the resulting withdrawal syndrome can be severe enough to require hospitalization. Review of postmarketing cases of precipitated opioid withdrawal in association with naltrexone treatment has identified cases with symptoms of withdrawal severe enough to require hospital admission, and in some cases, management in the intensive care unit.

To prevent occurrence of precipitated withdrawal in patients dependent on opioids, or exacerbation of a pre-existing subclinical withdrawal syndrome, opioid-dependent patients, including those being treated for alcohol dependence, should be opioid-free (including tramadol) before starting VIVITROL treatment. An opioid-free interval of a minimum of 7–10 days is recommended for patients previously dependent on short-acting opioids. Patients transitioning from buprenorphine or methadone may be vulnerable to precipitation of withdrawal symptoms for as long as two weeks.

If a more rapid transition from agonist to antagonist therapy is deemed necessary and appropriate by the healthcare provider, monitor the patient closely in an appropriate medical setting where precipitated withdrawal can be managed.

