#### 6. When Reversal of VIVITROL Blockade Is Required for Pain Management

In an emergency situation in patients receiving VIVITROL, suggestions for pain management include regional analgesia or use of non-opioid analgesics. If opioid therapy is required as part of anesthesia or analgesia, patients should be continuously monitored in an anesthesia care setting by persons not involved in the conduct of the surgical or diagnostic procedure. The opioid therapy must be provided by individuals specifically trained in the use of anesthetic drugs and the management of the respiratory effects of potent opioids, specifically the establishment and maintenance of a patent airway and assisted ventilation.

Irrespective of the drug chosen to reverse VIVITROL blockade, the patient should be monitored closely by appropriately trained personnel in a setting equipped and staffed for cardiopulmonary resuscitation.

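### Section 7.7 offers tramadol and buprenorphine for pain without the approval condition in 7.5 or the monitoring condition in the 2.3.1 warning, and prescribed buprenorphine for pain is left unresolved

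*Combined protocol and SAP*

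**What the plan says.** Three places in the protocol bear on pain relief while participants are under naltrexone blockade.

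- **Section 7.7 (rescue medications)** begins from the fact that naltrexone blocks opioids and then says that "participants requiring pain relief during the study period will be offered appropriate pain medications e.g., tramadol, regional blocks or partial opioid agonist such as buprenorphine". That sentence is the whole section.
- **Section 7.5 (prohibited medications)** treats opioids in separate entries. Buprenorphine, "either as part of a maintenance program or any illicit/non prescribed is prohibited for the duration of the study". Methadone has its own entry. All remaining opioids "are prohibited for the duration of the study unless approved by the PI or study clinician (see section 7.7").
- **Section 2.3.1, item 6 (warning text taken from the prescribing information)** reads: "In an emergency situation in patients receiving VIVITROL, suggestions for pain management include regional analgesia or use of non-opioid analgesics". It continues: "If opioid therapy is required as part of anesthesia or analgesia, patients should be continuously monitored in an anesthesia care setting". It also requires that the opioid be given by people trained in anesthetic drugs and in managing the respiratory effects of potent opioids.

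**The concern.** Section 7.7 is the operative instruction, the one that site staff would turn to when a participant has pain. It names two opioid agents and says that they will be offered, with nothing about who approves, in what setting, or under what observation. Conditions on these points stand elsewhere in the same protocol. Staff who work from 7.7 could give an opioid to a healthy volunteer under blockade without the safeguard that the protocol reproduces in its own risk section.

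There is also a question of conduct and records. Section 14.3 defines a deviation as any noncompliance with the protocol. Where the protocol does not settle whether a use is permitted, the site cannot classify that use consistently.

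**Working it through.** No arithmetic applies: the point depends on no rate, effect size or sample size. The check sets 7.7 beside 7.5 and 2.3.1, item by item.

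1. **Tramadol, 7.7 against 7.5.** Section 2.3.1, item 3, counts tramadol as an opioid: opioid-dependent patients "should be opioid-free (including tramadol) before starting VIVITROL treatment". That sentence is written for a different population and is used here only to classify the drug. Tramadol thus falls in the 7.5 entry for remaining opioids, which are prohibited unless the PI or study clinician approves. Section 7.5 cites 7.7 in that same sentence. Result: no contradiction. The gap is that the cross-reference leads to a section with no approver, no approval step and no documentation requirement.

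2. **Buprenorphine, 7.7 against 7.5.** The ban is worded for maintenance treatment and for illicit or non-prescribed use. Buprenorphine given by a clinician for pain is neither. The approval exception belongs to the entry for all other opioids, which follows the separate entries for buprenorphine and methadone, so it does not reach buprenorphine. Result: no literal contradiction, but 7.7 names a use that 7.5 neither clearly bans nor places under its approval route.

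3. **Monitoring, 7.7 against 2.3.1, item 6.** The warning does not rule opioids out. It attaches conditions to them: "patients should be continuously monitored in an anesthesia care setting", with suitably trained personnel. Section 7.7 names two opioids and carries none of these conditions. Result: a real mismatch between the operative text and the warning, within the scope limits discussed under the objection.

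4. **Non-opioid analgesics, 7.7 against 2.3.1, item 6.** In the warning, "suggestions for pain management include regional analgesia or use of non-opioid analgesics". Section 7.7 names no non-opioid analgesic. Its list is introduced as examples, so none is excluded. Result: an omission, not a conflict.

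5. **Regional techniques.** Section 7.7 names regional blocks and the warning names regional analgesia. Result: agreement.

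**The case against.** The strongest reply is that the protocol should be read as a whole. The approval step is stated in 7.5, in the very sentence that points to 7.7, and failing to repeat a condition is not the same as contradicting it. An offer made by a study clinician could itself be read as approval. The warning in 2.3.1 is label text under known risks, not a trial procedure. It concerns emergencies and offers suggestions, while 7.7 covers any need for pain relief. It also permits opioids under conditions, and the 7.7 list is open-ended.

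Most of this stands, and it limits the point. A reader might infer that 7.7 directly conflicts with the prohibited-medication section. The documents do not support that, for the reasons in items 1 and 2 of the working. A reader might also infer that the protocol describes pain relief under 7.7 as an overdose risk. The overdose warning in 2.3.1, item 1, concerns patients after detoxification, at the end of a dosing interval, after a missed dose or after stopping treatment, and people who try on their own to overcome the blockade with large amounts of opioids. It does not describe analgesia given by study staff to participants without a substance-related disorder.

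The reply does not supply what is missing. Reading 7.5 and 7.7 together still leaves prescribed buprenorphine for pain outside both the ban and the approval route. The emergency framing of the warning does not explain why the trial's own section on pain relief, which is not limited to non-emergency pain, says nothing about monitoring when it names opioids.

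**Conclusion.** The point holds in a limited form. Section 7.7 offers tramadol and buprenorphine without the approval condition that 7.5 attaches to other opioids and without the monitoring condition that 2.3.1, item 6, attaches to opioid use. It also names no non-opioid analgesic, although its list is not exhaustive. Section 7.5 leaves prescribed buprenorphine for pain undecided.

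The reach is narrow. The rule covers the whole study, but it operates only for participants who come to need pain relief, and a condition requiring opioid treatment is already an exclusion criterion in 5.2. The documents give no rate from which to estimate how many would be affected. The PK analysis plan and the sample size do not depend on the point.

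The conclusion assumes that 7.7 is meant to be usable by site staff as an instruction, and that the warning text is reproduced because the sponsor considers it relevant to these participants. On that footing this is a safety-related wording fault that should be corrected, not a defect in the analysis.

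**What to change.** The sponsor and the investigator should reconcile 7.7, 7.5 and item 6 of 2.3.1 so that a single consistent rule covers three matters: which agents may be used for pain, who approves them, and what monitoring applies. The reconciled text should state explicitly where buprenorphine prescribed for pain falls, so that its deviation status under 14.3 is clear. The cross-reference from 7.5 should lead to text that contains the approval condition or points back to it. Which agents, approvals or monitoring are right is a clinical decision, and none is proposed here.

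The cost is protocol wording, with no change to the visit schedule, PK sampling, sample size or analysis arising from this statistical review.

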## 7.8 PARTICIPANT ACCESS TO STUDY AGENT AT STUDY CLOSURE

N/A

## 7.9 REIMBURSEMENT COSTS

Participants will receive reimbursement as follows.

- \$50 for the screening visit
- \$50 for the consent visit
- \$200 for each inpatient day (4 days)
- \$50 for each scheduled outpatient visit (23 visits). Participants will receive an additional incremental bonus of \$10 for each subsequent visit attended (Visit 1: \$50, visit 2: \$50+\$10, Visit 3: \$50+\$20, Visit 4: \$50+\$30 ...). In case the scheduled visit is missed the value of the bonus is reset to the starting value of \$10. This schedule is designed to reinforce adherence to all study safety assessments.

The total amount of reimbursement should a participant attend every scheduled visit is \$4,580. If a participant is required to return for further PK or AE follow-up visits, or an unscheduled visit due to public health emergency then they will receive \$50. In addition, participants will also receive \$10 for transportation reimbursement.

## 8 ASSESSMENT OF SAFETY

### 8.1 SPECIFICATION OF SAFETY PARAMETERS

Safety will be assessed on the basis of:

- the incidence of death
- the incidence of SAEs
- the incidence AEs leading to discontinuation
- the incidence common AEs
- the incidence injection site reactions
- laboratory abnormalities indicating hepatic problems (absolute values and changes over time)

#### 8.1.1 *Definition of Adverse Events (AE)*

AEs will be identified from the telephone interviews, face to face visits or from the CRF. They will be recorded on an AE form.

##### 8.1.1.1 Definitions

An AE is any untoward medical occurrence in a clinical investigational participant administered a pharmaceutical product and which does not necessarily have a causal relationship with this treatment. An AE can therefore be any unfavorable or unintended sign (including an abnormal laboratory finding), symptom, or disease temporally associated with the use of a medicinal IP, whether or not considered related to the medicinal product. An adverse event is any adverse change (developing or worsening) from the patient's pre-treatment condition, including concurrent illness.

The investigator must make the distinction between exacerbation of pre-existing illness and lack of therapeutic efficacy.

#### 8.1.2 *Definition of Serious Adverse Events (SAE)*

A SAE is any adverse experience occurring during the study period that:

- results in death;
- is life-threatening;
- results in inpatient hospitalization or prolongation of existing hospitalization;
- results in a persistent or significant disability/incapacity; or
- results in congenital anomaly/birth defect.

A *life-threatening* AE is one that actually places the participant at immediate risk of death. A participant's reaction is not classified as life-threatening simply because more severe

manifestations of the same adverse reaction can be fatal, e.g., mild airway obstruction is not life threatening but severe airway obstruction is.

*Hospitalization* includes any inpatient admission, any transfer within a hospital for the purpose of treatment (for example, transfer of a participant from a psychiatric unit to a general medical unit) and prolongation of admission. Prolongation of hospitalization is defined as any extension of an inpatient hospitalization beyond the stay anticipated/ required in relation to the original reason for the initial admission, as determined by the investigator or treating physician.

Study coordinators will report any new SAEs to the PI, NYSPI IRB, DSMP and Sponsor within 24 hours of first knowledge.

## 8.2 CLASSIFICATION OF AN ADVERSE EVENT

### 8.2.1 *Severity of Event*

- **Mild** – Events require minimal or no treatment and do not interfere with the participant's daily activities.
- **Moderate** – Events result in a low level of inconvenience or concern with the therapeutic measures. Moderate events may cause some interference with functioning.
- **Severe** – Events interrupt a participant's usual daily activity and may require systemic drug therapy or other treatment. Severe events are usually potentially life-threatening or incapacitating.

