### 4. Hepatotoxicity

Cases of hepatitis and clinically significant liver dysfunction were observed in association with VIVITROL exposure during the clinical development program and in the postmarketing period. Transient, asymptomatic hepatic transaminase elevations were also observed in the clinical trials and postmarketing period. Although patients with clinically significant liver disease were not systematically studied, clinical trials did include patients with asymptomatic viral hepatitis infections. When patients presented with elevated transaminases, there were often other potential causative or contributory etiologies identified, including pre-existing alcoholic liver disease, hepatitis B and/or C infection, and concomitant usage of other potentially hepatotoxic drugs. Although clinically significant liver dysfunction is not

typically recognized as a manifestation of opioid withdrawal, opioid withdrawal that is precipitated abruptly may lead to systemic sequelae including acute liver injury.

Patients should be warned of the risk of hepatic injury and advised to seek medical attention if they experience symptoms of acute hepatitis. Use of VIVITROL should be discontinued in the event of symptoms and/or signs of acute hepatitis.

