#### 5.4.2.1 Participant Monitoring and Removal from Study

The psychiatrist and/or therapist will assess appropriateness for continuation in the research study on a continuous basis and will remove from the trial participants with significant clinical deterioration or noncompliance of a type which could be dangerous. Criteria for removal from the study will include:

1. Clinical deterioration which cannot be managed safely in the context of outpatient treatment. This would include a participant who becomes suicidal, or a participant who goes on drug binges (including non-opiate drugs).
2. Elevation of liver enzymes  $>3$  times normal. The PI or a study physician is available 24 hours/day by phone in case of emergency.

For those who withdraw from the study may request to withdraw from data collection and have no further contact with study site. Participants shall be informed that for a period of time 30 days after their last Vivitrol injection there may a risk that opioid based medication may have a reduced affect. There is no option to remove Vivitrol from a participant.

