#### ***10.4.5 Adverse Events***

After coding of AEs according to the Medical Dictionary for Regulatory Activity classification (MedDRA) and assignment to a system organ class and preferred term, all AEs recorded during the course of the trial will be listed by the participant number.

An AE will be considered as 'treatment emergent' if it occurred after the first drug administration of each period or if it was present prior to drug administration but exacerbated after the drug administration. All other adverse events will be considered "pre-treatment."

In the case where it is not possible to define an AE as being treatment emergent or not, the AE will be classified as treatment emergent as the most conservative approach.

A summary table describing all the TEAEs occurring during the trial will be produced overall and by treatment sequence using frequency of events and number and percentage of subjects experiencing these events. In addition, all TEAEs will be tabulated by intensity and relationship to drug in the same manner. Multiple occurrences of the same TEAE in one participant during the same treatment in the trial will be counted as multiple events in the frequency counts for adverse events. If a participant experiences more than one occurrence of the same TEAE during the same treatment in the trial, the participant will only be counted once using the worst severity and the strongest relationship.

All adverse events leading to trial or treatment discontinuation will be listed by treatment sequence and participant.

All SAEs will be listed by treatment sequence and participant.

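### The severity scale in section 8.2.1 has no laboratory criterion, so a symptom-free liver-enzyme rise of any size can be graded Mild, even above the plan's own >3x removal level

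*Combined protocol and SAP*

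**What the plan says.** All references are to the combined protocol and SAP.

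- **Laboratory findings can be adverse events.** Section 8.1.1.1 defines an adverse event to include "any unfavorable or unintended sign (including an abnormal laboratory finding), symptom, or disease temporally associated" with use of the product.
- **One severity scale serves all events.** Section 8.2.1 has three verbal grades. Mild begins "Events require minimal or no treatment and do not interfere with the" and ends with the participant's daily activities. Moderate reads "Events result in a low level of inconvenience or concern with the therapeutic measures" and adds possible interference with functioning. Severe requires interruption of the participant's "usual daily activity and may require systemic drug therapy or other treatment", and adds: "Severe events are usually potentially life-threatening or incapacitating". None of the three refers to a laboratory value.
- **The liver risk is known.** Section 2.3.1, item 4, states: "Transient, asymptomatic hepatic transaminase elevations were also observed in the clinical trials and postmarketing period". Sections 3.2 and 4.2.2 name hepatic effects as one of two types of event of special interest.
- **A liver-enzyme level has consequences elsewhere.** Section 5.4.2.1 lists "Elevation of liver enzymes" above 3 times normal as a criterion for removal. Section 5.2 excludes people whose ALT or AST is above 3 times the upper limit.
- **Severity feeds the analysis.** Under section 10.4.5, "all TEAEs will be tabulated by intensity and relationship to drug in the same manner", and a participant with repeated occurrences of an event is counted once, at the worst grade.

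**The concern.** The scale was written for symptoms. A raised transaminase is usually found on a blood test and need not be felt, so treatment need and daily function say little about how large it is. The plan warns that such silent rises occur with this product, and it treats one level of rise as enough to end participation. Yet its severity scale does not distinguish a trivial rise from one that crosses that level.

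What is at stake is the intensity table for an event type of special interest. A reader of that table could see only mild hepatic events in a study where a participant left because of liver enzymes. If some raters stretch the loose wording of the higher grades and others do not, the same ALT value could also receive different grades.

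**Working it through.** The plan gives no figure to reproduce. The check sets its definitions against one test case.

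**Step 1. Test case.** A liver-enzyme rise is recorded as an adverse event, without symptoms and without treatment. Section 2.3.1, item 4, makes this foreseeable.

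**Step 2. Apply section 8.2.1.**

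| Grade | What it asks | Does the case meet it? | Does height matter? |
|---|---|---|---|
| Mild | Little or no treatment, and no interference with daily life | Yes, both parts | No |
| Moderate | Inconvenience or concern tied to therapeutic measures; possible interference with functioning | Not clearly: there are no therapeutic measures and no loss of function | No |
| Severe, main criterion | Interruption of usual activity, possibly with treatment | No | No |
| Severe, added remark | Usually a potential threat to life, or incapacity | A rater could invoke it | Only by judgement; no level is stated |

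Take 1.1, 3.1, 8 and 20 times the upper limit as illustrations; these multiples are assumed and are not in the documents. All four fit Mild, and three of the four exceed 3 times.

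**Step 3. Look for a rule elsewhere.** No laboratory toxicity scale appears in the document. The causality scale in section 8.2.2 mentions abnormal laboratory results in three of its five categories (definitely, probably and unlikely related). The severity scale immediately before it mentions them in none.

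**Step 4. Effect on the intensity table.** Sections 4.1 and 5.3.1 allow up to 15 participants. Suppose one is removed for enzymes above 3 times normal, the event is graded Mild, and nobody has another hepatic event.

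- Removed for a hepatic finding: 1/15 = 6.7%
- Mild hepatic event in the intensity table: 1/15 = 6.7%
- Moderate or severe hepatic event: 0/15 = 0%

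The Protocol Summary still gives up to 6 participants; on that denominator the single case is 1/6 = 16.7%.

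**Step 5. Effect on duration by severity.** Section 8.3 asks for changes in severity to be documented so that time at each grade can be assessed. If a silent ALT rise goes from 1.1 to 8 times the limit and back, section 8.2.1 requires no change of grade, so this assessment could be empty for that event.

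**Step 6. Where the size would still be seen.**

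| Output | Shows size? |
|---|---|
| Intensity table (10.4.5) | Not necessarily |
| Counts outside the normal range (10.4.4) | No |
| Laboratory values and their change over time (3.2, 4.2.2, 8.1) | Yes |
| Listing of events leading to discontinuation (10.4.5) | Shows the removal |
| Individual safety data by time point (10.4.11) | Yes |

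**The case against.** The strongest reply has four parts.

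1. **The scale does not compel Mild.** Section 8.3 makes severity a clinician's assessment. Moderate mentions concern, and Severe mentions potential threat to life. This stands in part. The concern in Moderate is attached to therapeutic measures, which an untreated rise does not have, and the remark in Severe is qualified as usual rather than required. A higher grade is possible but never required.
2. **Other outputs keep the size.** Laboratory values, changes over time, discontinuation listings and individual tabulations would all show a large rise. This stands, and it limits the consequence to intensity reporting.
3. **A removal criterion and a severity grade serve different purposes.** One governs continued participation and the other describes intensity, so a precautionary removal can follow a low-intensity event. This also stands: the two sections do not contradict each other. The plan simply leaves their relation unstated, so a reader of the table cannot tell what Mild means for a liver enzyme.
4. **This is a small descriptive PK study.** It has one arm and no hypotheses (section 10.2), and no stopping rule uses the grade. That bears on how much the point matters. It is not a reason to leave the grading of laboratory events undefined.

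A reader might go further and infer that every silent rise must be graded Mild, or that the study's overall conclusion on liver safety would understate the harm. The first two replies show why the documents support neither inference.

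**Conclusion.** The point holds in a limited form. Section 8.2.1 gives no rule for grading laboratory adverse events. A symptom-free, untreated enzyme rise of any size can be graded Mild, and nothing in the plan requires more, including above the level listed for removal. The intensity table could then disagree in tone with the discontinuation listing for the same participant.

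The size is one participant's entry: 6.7 percentage points with 15 participants. This illustrates a single case and does not predict how often it would occur. It assumes that the rise is recorded as an adverse event, that it causes no symptoms and is not treated, and that the clinician follows the Mild wording.

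Detection, removal and the primary PK results are unaffected. This is an inexpensive improvement to the reporting of an event of special interest.

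**What to change.** - In section 8.2.1, keep the present functional scale for symptomatic events. Add that laboratory adverse events are graded by size, as multiples of the upper limit of normal, on a published laboratory toxicity scale that the sponsor names.
- State how those grades relate to the >3x level in sections 5.2 and 5.4.2.1. Section 5.2 names ALT and AST and refers to the upper end of the normal range; section 5.4.2.1 says only liver enzymes and normal. The two should be reconciled so that the grading has one reference.
- In section 10.4.5, use the size-based grade for laboratory events in the intensity table and in the worst-grade count per participant.
- Reconcile the liver function list in section 7.2.1, which names ALT but not AST, with the ALT or AST criterion in section 5.2.

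The cost is a paragraph or short table and a derivation from laboratory results. The ALT data are already planned; whether AST is measured must be settled first. The downside is that some laboratory events will be reported at a higher grade. The change concerns classification and reporting only and alters no removal rule or other clinical management. It should be made before events are graded and tabulated.
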